1.0 Objectives

1.1 *Describe the purpose, specific aims, or objectives of this research.*

Response:

Specific Aim 1: To determine the efficacy of Brief Behavioral Treatment for Insomnia (BBTI), experimental condition, compared to Healthy Eating Program (HEP), attention control, on insomnia severity in cancer survivors with insomnia.

Specific Aim 2: To determine predictors for efficacy of BBTI.

Specific Aim 3: To evaluate BBTI implementation with a focus on characterization of the patient- and provider-level facilitators and barriers.

1.2 *State the hypotheses to be tested, if applicable.*

NOTE: A hypothesis is a specific, testable prediction about what you expect to happen in your study that corresponds with your above listed objectives.

Response:

Hypothesis 1: Participants receiving BBTI will exhibit significant and durable improvement in insomnia severity index (key variable), sleep quality, mood, and functional status and quality of life measures over HEP.

Hypothesis 2: Selective demographics (older age), disease stage (stage I), treatment-related (surgery only), mood (nondepressed) and positive beliefs about sleep (needing less than 8-hours of sleep) will predict BBTI efficacy.

2.0 Scientific Endpoints

2.1 Describe the scientific endpoint(s), the main result or occurrence under study.

NOTE: *Scientific endpoints are outcomes defined before the study begins to determine whether the objectives of the study have been met and to draw conclusions from the data. Include primary and secondary endpoints. Some example endpoints are: reduction of symptoms, improvement in quality of life, or survival. Your response should **not** be a date.*

Response:

The scientific endpoints for this study are improvements in sleep, mood, functional status and quality of life.

3.0 Background

3.1 *Provide the scientific or scholarly background, rationale, and significance of the research based on the existing literature and how it will contribute to existing knowledge. Describe any gaps in current knowledge. Include relevant preliminary findings or prior research by the investigator.*

Response: Insomnia has devastating effects on health, function and well-being (1). Insomnia symptoms occur in one-third of the general population and 10-15% meet criteria for insomnia disorder, marked by chronic sleep disturbances that causes distress and impair their daytime functioning (2). Symptoms and side effects of cancer and cancer treatments render cancer survivors at increased risk for insomnia disorder (3-5). An estimated 40% of cancer survivors report sleep disturbances years after completing treatment (6). Consequently, interventions to address insomnia in cancer survivors are essential. Treatments for insomnia include pharmacologic and non-pharmacologic therapies that are equally efficacious; however, hypnotic medications such as benzodiazepine receptor agonists have potentially serious adverse effects including tolerance, drowsiness and cognitive impairment (7). Non-pharmacologic interventions, preferred by both patients and clinicians, include Cognitive Behavioral Therapy for Insomnia (CBTI), considered the “gold standard,” which requires expert training to deliver and multiple individual sessions (8, 9). Research in non-cancer populations revealed that CBTI is safe, efficacious, and durable (10, 11). However, CBTI is not widely available due to a lack of trained professionals and the high cost of treatment (12). Thus, a major gap in the field of oncology is an alternative to CBTI that is nurse-delivered, rigorously tested, low cost, durable, and having high treatment fidelity. Our preliminary data using Brief Behavioral Treatment for Insomnia (BBTI), a multicomponent intervention that integrates circadian science and behavioral principles of conditioned learning, revealed clinically significant improvements in insomnia severity, total sleep time, and sleep quality without the negative effects commonly reported with hypnotic medications in lung cancer survivors (13). Additionally, BBTI has been tested in several other pilot studies including older adults with chronic insomnia (14), treatment-resistant insomnia (15), and veterans with PTSD and insomnia (16). However, before BBTI is ready for translation into cancer nursing clinical practice, additional research on efficacy

and durability of BBTI is required. We hypothesize that exposing cancer survivors with insomnia to BBTI can help them self-manage their behavior to improve their sleep and quality of life.

Preliminary Studies The multidisciplinary team assembled for the current project has conducted four studies that involved a homogeneous sample of lung cancer survivors and patients receiving chemotherapy for advanced lung cancer(43-46). These studies established that lung cancer survivors (n=76) experienced middle insomnia (i.e., difficulty maintaining sleep) while patients receiving chemotherapy for lung cancer (n=50) had early (i.e., difficulty falling asleep) and middle (difficulty staying asleep) insomnia(43, 46). Additionally, these studies revealed that lung cancer patients with poor sleep scored significantly lower on measures of quality of life than lung cancer patients with good sleep(47). Eighty-five percent of patients with non-small cell lung cancer (NSCLC) in a longitudinal mixed method study had pre-existing insomnia related to anxiety, cancer- and treatment-related symptoms, and poor sleep hygiene practices(45).

The NIH-funded (1R15NR013779) pilot RCT involved lung cancer survivors who were more than 6 weeks post-surgery for stage I or II NSCLC and \geq 1-year since any other cancer treatment. Recruitment occurred during a routine survivorship clinic visit. Participants (n=44) were screened for sleep disorders with the Sleep Disorders Symptom Checklist(48), ApneaLink plus (AHI<15) and Insomnia Severity Index \geq 8. BBTI was manualized and content about the impact of melatonin, cortisol and nicotine on sleep for lung cancer survivors was added and the attention control intervention, Healthy Eating Program (HEP), was developed(13). No significant differences in baseline ISI were noted between groups ($p=0.11$). Posttreatment ISI mean score was $15.07 +/- 4.42$ for the control group and $6.94 +/- 5.27$ for the BBTI group ($p<0.001$; ES=1.61). Quality of life, using the Functional Assessment of Cancer Therapy-Lung (FACT-L), revealed nonsignificant baseline scores ($p=0.52$), but control group mean scores decreased ($74.67 +/- 26.40$) while BBTI group mean scores increased ($90.73 +/- 21.35$) which revealed a significant between group difference ($p<0.046$). Patients receiving BBTI improved FACT-L by 6.6 points and patients receiving the attention control declined by 14.5 points.

Taken together these previous studies confirm that insomnia was common in this homogeneous sample of cancer survivors. BBTI significantly reduced insomnia and improved quality and QOL at the post treatment measure. However, durability in the efficacy of BBTI was not assessed at 3-months or 12-months post-treatment. Additionally, current sleep literature does not include studies using BBTI in heterogeneous samples of cancer survivors with insomnia. This research team has the knowledge and experience to conduct and deliver the proposed RCT. In fact, this team includes researchers with expertise in the areas of nursing, medical oncology, pulmonary/sleep medicine and biostatistics. The NIH-funded PI is an advanced practice nurse with more than 20 years of clinical experience and 15 years of cancer-related fatigue, sleep and circadian rhythms and QOL research. The PI is collaborating with [name], DNS, RN, Professor and Chair of Biobehavioral Health and Clinical Sciences, University at

Buffalo, School of Nursing, a qualitative researcher, [name], a pulmonologist, sleep clinician and Co-Director of the University at Buffalo Sleep Fellowship Program; [name], Professor of Oncology, Roswell Park Comprehensive Care Center (RPCCC) and [name], Professor and Chair, Department of Biostatistics, University at Buffalo. The PI has an established record of collaboration with clinicians and researchers from RPCCC and the University at Buffalo, NY.

3.2 *Include complete citations or references.*

Response:

1. Institute of Medicine CoSMaR, Board on Health Sciences, Policy. *Sleep disorders and sleep deprivation: an unmet public health problem.* Washington, DC: National Academy of Sciences; 2006.
2. Ohayon MM. *Epidemiology of insomnia: what we know and what we still need to learn.* Sleep Med Rev. 2002;6(2):97-111. PubMed PMID: 12531146.

4.0 Study Design

4.1 *Describe and explain the study design (e.g. case-control, cross-sectional, ethnographic, experimental, interventional, longitudinal, observational).*

Response:

This is a longitudinal, randomized, efficacy trial. The experimental intervention, BBTI (attached), is being used to help participants with insomnia to sleep better. To receive this treatment, participants need to be enrolled in the study. The attention control intervention, HEP (attached), is not expected to improve sleep.

Baseline measures will be obtained prior to the intervention.

All of the multi-components of BBTI will be delivered individually in the clinic setting or online during a 45-minute session.

Outcome measures will be completed 1-month and again at 3-months and 12-months post-intervention. Each participant will complete one-week of: 1) Sleep diaries; 2) wrist actigraphy; and 3) a study packet with questionnaires on insomnia severity, sleep quality, insomnia symptoms, and beliefs about sleep, functional performance and quality of life. Additionally, two REDCap emails at 6-months and 9-months from the intervention will be sent to ensure patient safety and encourage participant retention. The emails will ask the participants to answer a safety question we currently ask at each previous data collection with a "Yes" or "No"

answer: Do you find that your sleepiness is bad enough that you are at risk of falling asleep while driving or doing something hazardous or harmful?

Additionally, we will ask 2 questions from the Sleep Diary about their sleep: Please rate over the past week: Restful sleep 0-4 (4=excellent) and Sleep quality 0-4 (4=excellent).

5.0 Local Number of Subjects

5.1 *Indicate the total number of subjects that will be enrolled or records that will be reviewed locally.*

Response:

The total number of subjects enrolled in the study will be 158, with 79 subjects from each group (intervention and attention-control group)

5.2 *If applicable, indicate how many subjects you expect to screen to reach your target sample (i.e. your screen failure rate).*

Response:

As the local study intends to enroll 158 participants, it is expected that 316 people will need to be screened.

5.3 *Justify the feasibility of recruiting the proposed number of eligible subjects within the anticipated recruitment period. For example, how many potential subjects do you have access to? What percentage of those potential subjects do you need to recruit?*

Response:

There are approximately 4,000 cancer survivors scheduled for care in the RPCCC' survivorship clinic annually. Half of these survivors will not be eligible for the study. That leaves approximately 2000 potentially eligible participants to recruit. As only 158 participants are needed over a 3-year recruitment period, the pool of survivors appears feasible.

6.0 Inclusion and Exclusion Criteria

6.1 *Describe the criteria that define who will be **included** in your final study sample.*

NOTE: This may be done in bullet point fashion.

Response:

1. Age \geq 18 years of age
2. \geq 1-month from surgery and \geq 1-month from any other treatment (except for hormone treatment or maintenance targeted therapies) for stages I through III: breast, colorectal, and prostate cancers and stages I through IV: lung cancer.
3. Meet published criteria for chronic insomnia: sleep latency $>$ 30 minutes or wake after sleep onset of $>$ 30 mins for \geq 3 nights/week for at least 1-month
4. ApneaLink Screening Apnea Hyponea Index $<$ 15

5. Ability to complete data collection instruments

6.2 *Describe the criteria that define who will be **excluded** from your final study sample.*

NOTE: This may be done in bullet point fashion.

Response:

1. Other pre-existing sleep disorders except insomnia or obstructive sleep apnea who are CPAP-compliant => 4-hours/night use
2. Unstable medical or psychiatric illness, fibromyalgia, history of seizures, current substance abuse
3. Engaged in night or rotating shift work
4. Travel across two or more time zones within 1 month prior to study participation
5. Inability to complete data collection measures independently
6. Individuals with conditions affecting the non-dominant arm (use of wrist actigraph)

6.3 *Indicate specifically whether you will include any of the following special populations in your study using the checkboxes below.*

NOTE: Members of special populations may not be targeted for enrollment in your study unless you indicate this in your inclusion criteria.

Response:

Not applicable: None of the following special populations will be recruited in the current study.

- Adults unable to consent
- Individuals who are not yet adults (infants, children, teenagers)
- Pregnant women
- Prisoners

6.4 *Indicate whether you will include non-English speaking individuals in your study.*

Provide justification if you will exclude non-English speaking individuals.

*In order to meet one of the primary ethical principles of equitable selection of subjects, non-English speaking individuals may **not** be routinely excluded from research as a matter of convenience.*

In cases where the research is of therapeutic intent or is designed to investigate areas that would necessarily require certain populations who may not speak English, the researcher is required to make efforts to recruit

and include non-English speaking individuals. However, there are studies in which it would be reasonable to limit subjects to those who speak English. Some examples include pilot studies, small unfunded studies with validated instruments not available in other languages, studies with numerous questionnaires, and some non-therapeutic studies which offer no direct benefit.

Response:

Persons who do not speak English are currently excluded from this research based on numerous questionnaires in this RCT.

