8.0 Eligibility Screening

8.1 Describe *screening procedures* for determining subjects' eligibility. Screening refers to determining if prospective participants meet inclusion and exclusion criteria.

 *Include all relevant screening documents with your submission (e.g. screening protocol, script, questionnaire).*

Response: Screening for inclusion criteria includes a YES response to the following questions:

Are at least 18 years of age?

Insomnia Severity Index>7 and/or Holland Sleep Disorders Screening Questionnaire>4.0

Do you have a diagnosis of breast, colorectal, or prostate cancer stage I, II or III; or lung cancer stage I-IV?

Have you had your cancer surgically removed at least 1-month ago?

Has it been more than one month since you completed cancer treatment (except for hormone treatment or maintenance targeted therapies)?

Screening for exclusion criteria includes a NO response to the following questions:

Do you have sleep disorders other than insomnia or obstructive sleep apnea who are CPAP-compliant => 4-hours/night use?

Do you have any poorly managed medical/psychiatric illnesses, fibromyalgia, or a history of seizures?

Are you currently exceeding alcohol or abusing drugs?

Do you engage in shift work or traveled >1 time zone past month?

Are you able to wear an actigraph on your non-dominant wrist?

1. The PI or Study Coordinator will use the Recruitment Script and Participant Eligibility Screening Form (instruments attached) to screen all eligible participants and the Holland Sleep Disorders Questionnaire (HSDQ), a valid, reliable and accurate diagnostic measure based on the International Classification of Sleep Disorder (ICSD-2) to determine the presence of insomnia, sleep apnea or any other sleep disorder. Depending on the scores, participants will be enrolled, require additional screening (sleep apnea) or referred to their provider for additional sleep disorders diagnoses.

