17.0 Data Management and Analysis

17.1 *Describe the data analysis plan, including any statistical procedures. This section applies to both quantitative and qualitative analysis.*

Response:

Specific Aim 1. The primary analyses involve the statistical assessment of Insomnia Severity Index (ISI) at 1 month and will be based on an analysis of covariance (ANCOVA) model. In taking this approach, we fit the dependent variable as a linear function of independent variables randomized treatment assignment, patient cancer type, the interaction between treatment assignment and cancer type, and baseline ISI level. Rather than utilizing the null distribution associated with the classic F-test for overall treatment differences within the ANCOVA framework, which is dependent on the validity of distributional assumptions, an exact permutation testing approach will be utilized. The randomization mechanism at work is a crucial component in this study in that it will be used to create the randomization distribution by which statistical significance will be determined. For more on this approach see Gail, Tan, and Piantadosi (1988)(120). Reported p-values will be obtained from the permutation distributions of the test statistics based on 10,000 Monte Carlo simulations. As additional analyses, subject covariates will be included as independent variables.

The interaction of treatment group and subject covariates may also be examined in a secondary fashion in order to identify possible differential effects of treatment. The analysis of secondary outcomes will proceed in a similar fashion. All statistical tests will be two-sided and tested at a 0.05 nominal significance level.

Specific Aim 2. Standard multiple regression will be used to determine predictors of efficacious response to BBTI. Standard diagnostic plots will be used to assess model fit and transformations of variables may be considered in order to meet statistical assumptions.

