Specific Aim 3. Evaluation of BBTI implementation focused on (a) characterization of the patient- and provider-level facilitators and barriers; and (b) knowledge/skills transfer among staff nurses using focus groups with each of the implementation facilitator groups. Transcript-based analysis, the most rigorous and accurate type of qualitative analysis, will be performed on focus group data. Audio recordings of each focus group meeting will be professionally transcribed verbatim and this text will provide the data for analysis. Prior to analysis, accuracy of the transcripts will be verified by [name]. The research team (Drs. [name] and [name]) will read all data repeatedly to achieve immersion and obtain a sense of the whole(121). Then data will be read by highlighting exact words that capture key thoughts or concepts. Next, the researchers will record first impressions, thoughts and initial analysis from the data. Labels for codes will emerge as the process continues. Codes may come directly from the text and become the preliminary coding scheme. Codes will be sorted into categories, which will be used to organize and group codes into meaningful clusters. Final codes will be organized into a hierarchical structure, if possible. Findings will be used to plan for dissemination and sustainability of this intervention. The software, Nvivo, will be used to assist in data management. During years 3 and 5, we will engage implementation facilitators and submit an IRB amendment before implementing aim 3.

17.2 If applicable, provide a power analysis.

NOTE: This may not apply to certain types of studies, including chart/records reviews, survey studies, or observational studies. This question is asked to elicit whether the investigator has an adequate sample size to achieve the study objectives and justify a conclusion.

Response:

The estimate of the variability used for sample size calculations was based on previous results, which showed the standard deviation to be approximately 4.8. Calculations show a sample size of 55 per group (110 total) will allow us to detect differences as small as 3 with 90% power. Since the actual analysis to be performed is based on a model, which incorporates baseline ISI and cancer type, which will account for some of the unexplained variability in the dependent variable, these calculations may be viewed as conservative. Based on our

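### Sections 6.2 and 8.1 admit people now in behavioural insomnia treatment and people from the team's own BBTI/HEP pilot, and Table 3 names no measure of either exposure

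*Combined protocol and SAP*

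**What the plan says.** **Eligibility.** Section 6.2 lists six exclusions. The one on sleep is "Other pre-existing sleep disorders except insomnia or obstructive sleep apnea who are CPAP-compliant", followed by a nightly-use threshold. The others cover illness and substance abuse, shift work, recent travel, ability to complete the measures, and conditions of the arm that wears the actigraph. The matching question in Section 8.1 is "Do you have sleep disorders other than insomnia or obstructive sleep apnea who are CPAP-compliant". Nothing in either section asks about behavioural treatment for insomnia, past or current, or about earlier BBTI studies.

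**The pilot.** Section 3.1 describes an earlier randomized pilot of the same two programs (n=44) in survivors of stage I or II non-small cell lung cancer. It states that "Recruitment occurred during a routine survivorship clinic visit". For that pilot BBTI was put into manual form and "the attention control intervention, Healthy Eating Program (HEP), was developed". Entry required ISI of at least 8 and an apnea-hypopnea index below 15.

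**The present pool.** Section 6.1 accepts lung cancer of stages I to IV and an index below 15. Section 8.1 screens on ISI above 7 and/or the Holland questionnaire. Section 5.3 draws on "approximately 4,000 cancer survivors scheduled for care in the RPCCC' survivorship clinic annually".

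**Data and analysis.** Table 3 (Section 10.2) lists sleep history, medications and comorbidities at baseline, but no item on behavioural insomnia treatment. The primary model in Section 17.1 is an ANCOVA of 1-month ISI on treatment, cancer type, their interaction and baseline ISI.

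**The concern.** Followed as written, the criteria admit two groups whose response may not reflect a first exposure to BBTI or HEP.

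The first is people in CBTI at entry. Assigned to HEP, such a person is receiving an active insomnia treatment while counted as a control. Assigned to BBTI, they have less room to gain from it.

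The second is people from the pilot. Those who had BBTI already know its content. Those who had either program have seen one of the two before rating a self-reported primary outcome.

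In both arms the likely result is a smaller difference between BBTI and HEP, and so lower power for Aim 1. Aim 2 is also touched: beliefs about sleep are a hypothesized predictor of response, and earlier BBTI or CBTI could have changed them before baseline. Because Table 3 names no measure of the exposure, the analysis could not identify these participants later.

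**Working it through.** **1. Can pilot participants qualify again?** The entry rules compare as follows.

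| | Pilot (3.1) | This trial (6.1, 8.1) |
|---|---|---|
| Lung cancer stage | I–II | I–IV |
| ISI | at least 8 | above 7 (the same cut on an integer scale) and/or Holland questionnaire |
| Apnea-hypopnea index | below 15 | below 15 |
| Source | a survivorship clinic | mainly the Roswell Park survivorship clinic |

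Pilot post-treatment ISI was 15.07 (SD 4.42) for controls and 6.94 (SD 5.27) for BBTI. Under a normal approximation, the share above the cut is Φ((mean − c)/SD), with c = 7, or 7.5 with a continuity correction:
- HEP: (15.07 − 7)/4.42 = 1.83, or 1.71 at 7.5, giving about 97% or 96%.
- BBTI: (6.94 − 7)/5.27 = −0.01, or −0.11 at 7.5, giving about 50% or 46%.

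So the ISI screen alone would not keep them out. They would still have to meet the chronic-insomnia criterion in Section 6.1.

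**2. Reproduce the planned sample size.** Section 17.2 gives the SD, "which showed the standard deviation to be approximately 4.8", and claims that "a sample size of 55 per group (110 total) will allow us to detect differences as small as 3 with 90% power". Section 17.1 sets two-sided 0.05.
- n per group = 2(1.960 + 1.282)² × 4.8² / 3² = 53.8, so 54. The t-test version gives 54.8, so 55.
- Power at 55 per group = Φ(3/(4.8√(2/55)) − 1.960) = 0.906 (t-test 0.901).
- 110/(1 − 0.30) = 157.1. Rounding up per arm, 55/0.70 = 78.6, so 79 and 158 in total.

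The plan's figures reproduce. There is no arithmetic error.

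**3. Illustrate dilution.** Let p be the share of each arm that contributes no BBTI-versus-HEP contrast, with the SD unchanged. The expected difference is 3(1 − p). The documents do not give p, so the values below are assumptions.

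| p (assumed) | Difference | Power at 55 per group |
|---|---|---|
| 0 | 3.00 | 0.906 |
| 2% | 2.94 | 0.895 |
| 5% | 2.85 | 0.876 |
| 10% | 2.70 | 0.839 |

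Zero contrast is an upper bound for past treatment. It is closer to the mark for treatment under way at entry.

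**4. How many could the pilot supply?** The pilot's allocation is not stated. On an assumed equal split, 22 had BBTI, and 46% to 50% of 22 is 10 to 11 above the ISI cut. Even if all 11 enrolled, that is 11/158 = 7.0%. With no contrast from any of them, the difference would be about 2.79 and power 0.86. Actual numbers would very probably be lower.

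**The case against.** Several points on the other side have force.

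- **Exposure is probably rare.** Section 3.1 describes CBTI as scarce and costly, and Section 4.1 says BBTI is obtainable only by enrolling. This stands as a limit on size. Neither statement is an eligibility rule, and the second does not cover people treated in the pilot.
- **Past treatment is partly absorbed.** Entrants must have insomnia now, and the model adjusts for baseline ISI. This stands for past treatment, less so for treatment in progress.
- **The planned effect may be cautious.** The pilot difference was 15.07 − 6.94 = 8.13 points. Diluted by 10% it would still be 8.13 × 0.9 = 7.3. Section 17.2 also notes that covariates were ignored. If the true effect is near the pilot's, the power loss is negligible.
- **Unseen attachments may cover it.** The eligibility screening form, the recruitment script and the medical record questionnaire are not in the text and might ask about treatment. The protocol's own criteria do not.
- **The pilot's clinic is not named.** Overlap with the present pool is therefore an inference.

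A reader might also infer four stronger conclusions that the documents do not support:
- *Up to 44 of 158 participants could be already treated.* The 44 includes the HEP arm, whose members did not receive BBTI there.
- *The control arm is biased relative to BBTI.* Randomization balances prior exposure on average.
- *Pilot participants defeat the masking.* No passage describes participant masking, or says that pilot participants were told which program was the comparator.
- *All prior CBTI should be excluded.* That would trade away generalizability to survivors whose insomnia persisted after treatment, and the documents give no reason to require it.

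**Conclusion.** The gap is real. The criteria as written admit people in current behavioural insomnia treatment and former pilot participants, and Table 3 names no measure that would identify them. The expected harm is a diluted contrast and some loss of power in both arms. It does not invalidate the primary comparison.

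The size cannot be fixed from the documents. Over an assumed no-contrast share of 2% to 10%, the 3-point difference shrinks by 0.06 to 0.30 points, and power falls from about 0.91 to between about 0.90 and 0.84. This rests on the planning values in Section 17.2, an unchanged SD and zero contrast in those affected. The low end is more plausible, given how scarce CBTI is said to be. The point merits action because the remedy is cheap, not because a large loss has been shown.

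**What to change.** 1. Add two exclusions to Section 6.2 and matching questions to Section 8.1: (a) participation in the earlier BBTI/HEP pilot, checked against pilot enrolment records where the team still has them; (b) current behavioural treatment for insomnia.
2. Add to Table 3 an item on prior CBTI or BBTI at baseline, and an item on behavioural insomnia treatment outside the study at 1, 3 and 12 months. Do not exclude people for prior CBTI.
3. Keep anyone already randomized in the primary analysis. Report one sensitivity analysis without those known to have met (a) or (b) at entry. Both are pre-randomization characteristics, so leaving those people out does not select on response. Treatment begun during follow-up should be described, not used to drop participants.

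The cost is two or three questions and a slightly smaller pool. Section 5.3 puts about 2,000 potentially eligible survivors against 158 places (158/2,000 = 7.9%), so recruitment should hardly be affected. The sample size stays at 55 evaluable per group and 158 enrolled.
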